5.3.2 RANDOMISATION

Once tolerance to ¼ boiled peanut has been demonstrated, the participant will be randomised using an online randomization tool (www.sealedenvelelope.com). Randomisation will be blocked (using random permuted blocks) to ensure that the groups are balanced, and include a level of stratification according to whether the child is predominantly sensitized to a specific peanut protein components (Ara h 2). Pilot data indicates that the boiling process affects Ara h 2 content more than other peanut proteins. Thus, patients who are predominantly sensitized to Ara h 2 may be more likely to have a successful outcome than those allergic to other peanut proteins.

The Ara h 2 predominant Phenotype is defined as:

- Specific IgE to Ara h 2 > 1.0 kUA/l
- Specific IgE to Ara h 1 and Ara h 3 <1.0 kUA/l

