5.8.2 QUALITY OF LIFE ASSESSMENTS

The impact of OIT on participants' quality of life (QoL) will be assessed both from parents' and participants' perspective using abbreviated versions of disease-specific validated "food-allergy quality of life questionnaire" (FAQL-Q) in its parental, ¹⁴ child¹⁵ and teenage¹⁶ forms at baseline, 3, 6, 12, 24 and 36 months in both the active and control groups. These new abbreviated versions have been validated (data submitted for publication). We will also assess the impact of the child's food allergy on parent QoL, using the FAQL-Parent Burden form (which has been validated in a UK population).¹⁷ QoL assessments will be done both prior to and after oral challenges.

The FAQL-questionnaires are based on a 7-point Likert scale and changes greater than 0.5 points over time have been defined as clinically significant. Previous studies have reported a positive effect on QoL following OIT to peanut from the parents' perspective, however, there are no controlled studies which have addressed the impact on QoL as perceived by participants. This is a significant knowledge gap, since there is a concern that while parents report an improved QoL when their child undergoes OIT, the child themselves may experience a worsening of QoL due to frequent side effects and need to alter their activities following OIT doses.

In line with current expert opinion, and to ensure the ability to compare responses consistently during the first 12 months of OIT, children who are age 12 at study commencement will be asked to complete the Teenage versions of the QoL assessments, unless there are difficulties with comprehension which preclude this.

We will also assess parental anxiety before, and 12 and 24 months after their child commencing OIT, using the Perceived Stress Scale.¹⁹

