7.2 STATISTICAL ANALYSIS PLAN

Data will be collected on paper CRFs which include the patients name, DOB and hospital number. Participants will be assigned a study number, which will be noted on the paper record. Data will then be entered on to a password-protected computer database on the secure hospital IT system; only the study number will be used to identify the patient data.

De-identified data and all appropriate documentation will be stored for a minimum of 10 years after the completion of the study, including the follow-up period.

The primary analysis will be performed on an intention to treat basis: all subjects allocated to each arm will be analysed together as representing that treatment arm, irrespective of compliance and whether or not they have completed the prescribed regimen. A secondary analysis will also be performed on a per protocol basis.

Subjects who are withdrawn from active treatment will remain in the study for assessment of outcome relating to QoL measures.

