7.2.1 ANALYSIS OF PRIMARY ENDPOINT

The primary analysis will compare the proportion of subjects who tolerate 1.4g (or more) roasted peanut protein in the active and control groups, 12 months after randomization, using a two-sided Fisher's exact test at a p<0.05 level of significance.

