7.2.2 ANALYSIS OF SECONDARY ENDPOINTS

The following secondary analyses will be performed, using two-sided testing for non-parametric data at a p<0.05 level of significance:

- Relative change in clinical threshold (NOAEL, LOAEL) to roasted peanut at 6 and 12 months in active vs control, using Mann-Whitney U test.
- Proportion of subjects who tolerate 1.4g (or more) roasted peanut protein in the active and control groups, 12 months after randomization and following cessation of all peanut intake for 4 weeks after 1 and 3 years of OIT, using a two-sided Fisher's exact test at a p<0.05 level of significance.
- Change in quality of life assessments before, and at 6 and 12 months after OIT, as assessed by FAQL-Questionnaire in children, teenagers and their parents in the active vs control groups using paired and group comparisons by non-parametric testing.
- The incidence of adverse events experienced between active and control groups. Statistical differences will be
 determined using Fisher's exact test for proportions or using non-parametric tests for graded reactions.
 Logistic regression will be used to assess the influence of age, gender, asthma status and prior history of
 anaphylaxis on incidence of adverse events.
- Immunological outcome measures pre-, during and post- 12 months of OIT, using Mann-Whitney U test (for paired comparisons) or Friedman's test (for trends over time).

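### Analysing FAQL-Q with the baseline score as a covariate would gain a little precision at almost no cost; the planned comparison of change is valid

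*Combined protocol and SAP*

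**What the plan says.** Section 5.8.2 schedules FAQL-Q "at baseline, 3, 6, 12, 24 and 36 months in both the active and control groups". It uses parent, child and teenage forms on a 7-point scale, and adds that "changes greater than 0.5 points over time have been defined as clinically significant". It also states that "QoL assessments will be done both prior to and after oral challenges".

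Section 7.2 keeps children who stop treatment in the QoL follow-up: "Subjects who are withdrawn from active treatment will remain in the study for assessment of outcome relating to QoL measures". The intention-to-treat rule for the primary analysis is that "all subjects allocated to each arm will be analysed together as representing that treatment arm".

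Section 7.2.2 compares change at 6 and 12 months "in children, teenagers and their parents in the active vs control groups using paired and group comparisons by non-parametric testing". It names no baseline covariate and does not say which baseline or 12-month score is used. The only covariate model in section 7 is a logistic regression for adverse events.

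Randomisation is stratified by Ara h 2 predominance because "patients who are predominantly sensitized to Ara h 2 may be more likely to have a successful outcome" (section 5.3.2). Section 7 does not mention the stratum. The primary test compares proportions "in the active and control groups, 12 months after randomization, using a two-sided Fisher's exact test at a p<0.05 level of significance".

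**The concern.** A change score removes the whole baseline value, whereas the follow-up score predicts only a fraction r of it. A chance baseline difference between arms therefore carries (1 - r) of its size into the comparison of change, with the sign reversed. ANCOVA estimates the right fraction from the data.

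This matters more when groups are small. The trial has 46 children at 2:1, and FAQL-Q is further split by questionnaire form. Section 5.8.2 calls the participant's own view of QoL a significant knowledge gap, so precision on this outcome has value.

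There is also an ambiguity. With QoL taken before and after challenges, more than one score can exist at baseline and at 12 months. A post-challenge score may reflect the challenge result.

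**Working it through.** **Inputs from the documents.** 30 active and 16 control, 20% loss, 60% v 10% success (section 7.1); two-sided 0.05; 0.5-point threshold (section 5.8.2). Evaluable numbers: 30 x 0.8 = 24 and 16 x 0.8 = 12.8, taken as 13.

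**Assumed, because the documents are silent.** r = 0.5, 0.7, 0.8; SD 1.3 points; 12 v 6 for a single questionnaire form.

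**The plan's own figure.** No sample size is given for FAQL-Q. For the primary endpoint, the continuity-corrected formula at 2:1 gives 38.2 evaluable. That becomes 45.9 when multiplied by 1.2, or 47.8 when divided by 0.8, against the stated 46. Exact Fisher power is 85.3% at 24 v 13 and 93.4% at 30 v 16. The primary design is not in question.

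**Variance.** With equal SDs at both visits, a change score has variance proportional to 2(1 - r) and ANCOVA to (1 - r²), so the ratio is (1 + r)/2. Estimating the slope multiplies this by 1 + 1/(N - 4), which is 1 + 1/33 at N = 37.

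| r | (1 + r)/2 | x 34/33 | Variance cut |
|---|---|---|---|
| 0.5 | 0.75 | 0.773 | 23% |
| 0.7 | 0.85 | 0.876 | 12% |
| 0.8 | 0.90 | 0.927 | 7% |

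Simulation agrees: ratios of about 0.77 and 0.88 at r = 0.5 and 0.7, and 0.93 to 0.95 at r = 0.8 (a cut of 5 to 7%).

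**Chance baseline imbalance.** One standard error is sqrt(1/24 + 1/13) = 0.344 SD at 24 v 13, and sqrt(1/12 + 1/6) = 0.500 SD at 12 v 6. The shift in the change comparison is (1 - r) x SE x 1.3:

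- r = 0.5: 0.5 x 0.344 x 1.3 = 0.22 points; 0.5 x 0.500 x 1.3 = 0.33 points.
- r = 0.8: 0.2 x 0.344 x 1.3 = 0.09 points; 0.2 x 0.500 x 1.3 = 0.13 points.

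It can go either way and averages to zero.

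**Power for a 0.5-point effect.** Rank test on change v ANCOVA with a re-randomisation p-value, simulated on a bounded scale with SD 1.3:

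| r | 24 v 13 | 12 v 6 |
|---|---|---|
| 0.5 | 18.0% to 23.1% | 9.5% to 12.2% |
| 0.7 | 26.3% to 31.6% | 13.7% to 16.5% |
| 0.8 | 37.4% to 42.3% | 18.4% to 20.3% |

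The gains are about 5 points and 2 to 3 points. An unbounded normal model with ordinary ANCOVA gives about 6 points at 24 v 13 (17.4% to 23.5% at r = 0.5). Part of this comes from leaving ranks: a t-test on change already reaches 19.3% there. Null rejection of the re-randomisation ANCOVA was 4.5% to 5.8%.

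**Unequal slopes.** At 24 v 13 with a 0.5 SD effect, slope and residual SD of 0.6 and 0.8 in the active arm, and 0.95 and 0.3 in controls, power was about 52% for the rank test on change and 53% for ANCOVA.

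**The case against.** The strongest reply is that this is a preference. FAQL-Q is one of several secondary outcomes, the analysis text is brief, and reading it as a rank test on change is plausible but inferred. The size is wholly assumed. At the plan's own threshold the comparison stays underpowered either way, and the gain shrinks towards nothing within a form or with unequal slopes. Section 5.8.2 itself raises the possibility that OIT worsens some children's QoL, so unequal slopes are not far-fetched. All of this stands and limits the point to a suggestion.

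Three stronger readings are tempting, and the documents do not support them.

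- *A reader might infer that the change comparison is biased or invalid.* It is not. Arms are randomised, and the imbalance effect is zero on average.
- *A reader might infer that the primary test should be stratified because randomisation was.* Fisher's test remains valid. Across assumed stratum shares and success gaps, an exact stratified test ranged from a loss of about 2 points of power to a gain of about 2.5. The stratified and crude risk differences had the same standard error (0.129 at 24 v 13, one third in the stratum, 40-point gap). There is no case for adding either.
- *A reader might infer that success rates by stratum would show whether the reason for stratifying holds.* Numbers are too small. With 60% success overall among 24 treated children and a 40-point gap between strata, Fisher power is 22% (6 v 18), 36% (8 v 16) or 39% (12 v 12). The topic is not ignored either: section 2.2 has an objective on predictors of success, and section 5.8.3 measures component antibodies, although section 7 gives no method for that objective.

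**Conclusion.** The point holds as a low-severity improvement. Section 7.2.2 uses a baseline score that the trial already collects less efficiently than it could, and leaves open which scores are compared. With equal slopes, ANCOVA lowers the variance at 24 v 13 by roughly a quarter to a twentieth as r goes from 0.5 to 0.8. These gains depend on the assumed SD, r and numbers per form. The more certain benefits are a defined baseline and outcome, and an estimate with a confidence interval to read against 0.5 points. For Ara h 2, the only gap worth closing is descriptive.

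**What to change.** **Section 7.2.2.** Compare 6- and 12-month FAQL-Q between arms, within each questionnaire form, by ANCOVA with the baseline score as covariate.

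- Define baseline as the pre-challenge, pre-randomisation score, and the 12-month outcome as the pre-challenge score. Apply the same rule at 6 months wherever a challenge is held at that visit.
- Report the adjusted difference in points with its 95% CI beside the 0.5-point threshold.
- To stay distribution-free, take the p-value by re-randomisation that follows the actual allocation: Ara h 2 strata with permuted blocks. State how the interval is obtained so that it agrees with that p-value.

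**Section 7.2.1.** Keep Fisher's test as primary. Add one table of success by arm within Ara h 2 stratum, labelled as description only.

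**Cost.** No new data; one degree of freedom; a rule for missing baseline scores. A visit window is also needed, because families of children withdrawn after a significant reaction are contacted 1 and 6 months after the event (section 5.8.2), which may miss the 6- and 12-month dates. Section 7 is part of the protocol, so this is an amendment. As the trial is open label, it should precede analysis of the 12-month QoL data. Amendments run from 2015 to 2018, so some of those data may already exist, and the amendment should state whether they have been examined.

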4. STUDY POPULATION

4.1. INCLUSION CRITERIA

- 1. Age 8-16 years.
- 2. Past history of peanut allergy, with:
 - Previous clinical reaction with ongoing sensitisation to peanut, OR positive allergy test to peanut (either skin prick test ≥8mm or serum specific IgE > 15kUA/I) to peanut consistent with >95% likelihood of clinical allergy⁹, AND
 - further confirmation of clinical reactivity to roasted peanut at double-blind placebo-controlled food challenge at screening
- 3. Tolerates at least ¼ boiled peanut (boiled for 4 hours) at open food challenge at screening.
- 4. Full informed consent of parent/legal guardian and patient assent.

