5.3.4 ACTIVE GROUP: ORAL IMMUNOTHERAPY

Subjects randomized to the active intervention arm will continue to undergo an OPEN (unblinded) food challenge at the same visit, to determine the starting dose of boiled peanut. This is because some children may exhibit a degree of *de novo* tolerance to boiled peanut, and thus demonstration of tolerance allows for individualization of the updosing protocol. The open challenge will utilize the following protocol:

Protocol 2: Open OFC to boiled PN	Boiled peanuts (If dose tolerated, commence		
TIME POINT (mins)	No. peanuts Peanut protein (mg)*		updosing at STEP:	
(Already given in 5.3.1)	¼ boiled peanut	30	pre-A	
0	¾ boiled peanut	100	1	
30	2 boiled peanuts	260	1	
60	4 boiled peanuts	520	1	
90	8 boiled peanuts	1040	5	
Cumulative dose 15 boiled peanuts 1950				
2 hours observation period following last dose to monitor for signs of reaction				

^{*}Boiled peanuts contain approximately half the amount of protein as roasted peanuts.

The criteria listed in Section 5.2.2 will be used to determine outcome of this food challenge.

Children will receive daily doses of peanut at home, initially using boiled peanut. The updosing regime is shown in Table 1. Children who tolerate at least 1 boiled peanut will commence updosing at ½ boiled peanut, unless they have passed the challenge in its entirety (i.e. tolerates 15 boiled peanuts) in which case they will commence at STEP 5. Those who tolerate ¼ boiled peanut only will commence updosing at the pre-A step (Table 1).

Children in the ACTIVE group (and their parents) will undergo quality-of-life assessments at 0, 3, 6 and 12 and 24 months (see section 5.7.1).

Prior to discharge home, each family will be provided with:

- A symptom advice sheet (including advice on avoiding intense physical exercise up to 2 hours after the dose intake).
- A food allergy management plan (Figure 6), including an emergency medicine kit containing non-sedating oral
 antihistamine and two adrenaline auto-injectors. Where the child has a history of asthma or prior respiratory
 symptoms to a food allergen, the kit will also include a salbutamol inhaler and spacer device. Families and
 participants will be instructed in the prompt recognition and treatment of allergic reactions, including
 adrenaline auto-injectors.

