5.3.4.4 PREPARATION OF BOILED AND ROASTED PEANUT FOR OIT

Families will be provided with blanched raw peanut at hospital visits, for preparation at home. Full instructions will be provided (as part of the **home diary and instruction sheet**). Peanuts (Holt Runner cultivar, supplied by the Peanut Company of Australia Ltd) will be supplied in 125g vacuum-packed batches to families on an as-needed basis, in order to monitor peanut consumption.

Families will be provided with instructions to boil the peanuts at home in batches, as follows:

- Boil 100g quantity of peanuts in a saucepan in ~600ml water for xx hours
- Drain and plunge peanuts into cold water, then drain in colander/sieve
- Lay peanuts in a single layer on a baking tray lined with baking paper
- Place tray in freezer until peanuts are 'snap frozen'
- Transfer peanuts into a plastic container and store in freezer until required.

The boiling time will be progressively reduced as depicted in Table 1 above.

In those children who tolerate roasted peanuts, families will be instructed to use commercial roasted peanuts (KP roasted peanuts) sourced from a UK supermarket. Alternatively, peanut M&Ms may be substituted for roasted peanut, where this is desired by the study participant: four roasted peanuts is equivalent to 6 peanut M&Ms.

5.4 1 YEAR ASSESSMENT

All subjects, in both the active (OIT) and control groups, will be invited to undergo a further DBPCFC to roasted PN at 12 months. Those who tolerate >1.4g of peanut protein at this challenge will be invited back for a further open challenge having stopped all peanut ingestion (including OIT doses) for 4 weeks. The challenges and outcomes are depicted in summary form in Figure 7.

[figure not shown]

Figure 7: Challenges and outcomes, months 12-13

All subjects will also undergo repeat skin prick testing to commercial crude peanut extract, and quality-of-life assessments as described in section 5.7.1.

Imperial College

5.4.1 12 MONTH DBPCFC

The DBPCFC will be performed as per Protocol 1 in Section 5.2.2. The purpose of this challenge is:

- In those who have undergone OIT, to assess for desensitisation to roasted peanut and a resulting change in threshold of clinical reactivity (Primary and Secondary outcome measures).
- In the control group, to determine the rate of natural resolution of peanut allergy and for those continuing into WP2 (where they will undergo OIT), serve as the baseline threshold of clinical reactivity to roasted peanut.

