6. ADVERSE EVENT REPORTING

6.1 DEFINITIONS

An adverse event is any occurrence or worsening of an undesirable or unintended sign, symptom, laboratory finding, or disease that occurs during participation, including occurrences that are not necessarily caused by or related to a study intervention. An adverse event will be followed until it resolves or until 30 days after a participant terminates from the study, whichever comes first.

A **serious adverse event** (SAE) is defined as any adverse event that suggests a significant hazard. This includes but is not limited to any of the following:

- 1. Death: Any death that occurs during the study must be reported whether considered treatment related or not.
- 2. A life-threatening event: Any adverse therapy experience that, in the view of the investigator, places the participant at immediate risk of death from the reaction as it occurred.
- 3. Inpatient hospitalization or prolongation of existing hospitalization.
- 4. Persistent or significant disability.
- 5. An event that requires intervention to prevent permanent impairment or damage. An important medical event that may not result in death, be life threatening, or require hospitalization may be considered an SAE when, based on appropriate medical judgment, it may jeopardize the participant and may require medical or surgical intervention to prevent one of the outcomes listed above.
- 6. Important AEs that are not immediately life-threatening or do not result in death or hospitalization but may jeopardise the subject or may require intervention to prevent one of the other outcomes listed in the definition above, should also be considered serious.

The adverse event can be described as 'expected' if it caused symptoms and/or signs that could be reasonably described as a consequence of an allergic reaction to peanut exposure within the protocol. Symptoms of an allergic reaction are defined as any described within this protocol.

An adverse event is considered "unexpected" when its nature or severity is not consistent with the investigator's protocol.

An adverse event is defined as "**related**" when it has resulted from the administration of any of the research procedures. Related adverse events are defined as "**adverse reactions**".

Any symptoms requiring treatment for anaphylaxis (adrenaline, steroids, salbutamol) following an OIT dose will be classified as a SERIOUS ADVERSE REACTION.

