6.2 DOCUMENTATION OF ADVERSE EVENTS

All adverse events will be recorded on a specifically designated case report form (CRF) from the time the participant provides consent until the time the event resolves or until 30 days after the participant completes study treatment. Adverse events may be discovered through observing and questioning the participant or receiving an unsolicited complaint and questioning the participant in an objective manner. All adverse events will be recorded, regardless of their severity or relation to study medication or procedures.

All serious adverse events (SAEs) will be reported on a SAE report form in addition to CRFs. Safety data will be reviewed at least every four months by the Independent Data Monitoring Committee (IDMC). The IDMC has the authority to recommend withdrawal of a study participant or termination of the trial because of safety findings.

All SAEs should be reported to the Research Ethics Committee, where in the opinion of the Chief Investigator, the event was:

- 'related', ie resulted from the administration of any of the research procedures; and
- 'unexpected', ie an event that is not listed in the protocol as an expected occurrence

Reports of related and unexpected SAEs should be submitted within 15 days of the event, using the NRES SAE form for non-IMP studies. The Chief Investigator must also notify the Sponsor of all SAEs.

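### The between-arm adverse-event comparison has no time window and no rule on food-challenge reactions, so on the plan's own definitions it is uninformative or measures the wrong thing

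*Combined protocol and SAP*

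**What the plan says.** - **Section 7.2.2** lists, among the secondary analyses, "The incidence of adverse events experienced between active and control groups". Differences are to be "determined using Fisher's exact test for proportions or using non-parametric tests for graded reactions". Logistic regression is to relate adverse-event incidence to age, gender, asthma and prior anaphylaxis. No window or event subset is stated, although other items in the same section do give time points.
- **Section 6.1** defines an adverse event broadly, "including occurrences that are not necessarily caused by or related to a study intervention". An event is related "when it has resulted from the administration of any of the research procedures", which covers a food challenge.
- **Section 6.2:** "All adverse events will be recorded on a specifically designated case report form (CRF) from the time the participant provides consent". Section 5.1 places consent at the first screening visit.
- **Section 4.1** requires "further confirmation of clinical reactivity to roasted peanut at double-blind placebo-controlled food challenge at screening". Section 5.3 puts that positive challenge before randomisation.
- **Section 5.4:** both arms "will be invited to undergo a further DBPCFC to roasted PN at 12 months".
- **Section 5.3.4:** "Subjects randomized to the active intervention arm will continue to undergo an" open boiled-peanut challenge. The active arm also has the open roasted-peanut challenge at transition (5.3.4.2), and its responders have one at 13 months (5.4.2). Controls have none of these in the first 12 months.
- **Section 3.2** gives the purpose of the contrast: OIT against controls who may have accidental reactions.

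**The concern.** A food challenge is meant to provoke a reaction in an allergic child. If those reactions enter the safety comparison, it reflects who was challenged and who became desensitised, as well as what OIT did. Safety is a secondary objective (2.2), an acceptable safety profile is part of the hypothesis (1.2), and safety is one stated reason for having a control arm (3.2). A null result, or one in favour of OIT, that came from the challenge schedule could be read as reassurance about a treatment given to children. Because the trial is open label, an undefined event set could also be chosen after the data are seen.

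**Working it through.** **The plan's own figure.** The documents give no expected rate or power for the adverse-event comparison. The only stated figure is the total of 46 (section 7.1), which supplies the rates used below. Inputs: 10% v 60%, 2:1, two-sided 0.05, 80% power, continuity correction. With k = 2, d = 0.5 and pooled p = (0.1 + 2 × 0.6)/3 = 0.433:

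- Control n₀ = [1.96√(p(1−p)(1+1/k)) + 0.842√(0.1×0.9 + 0.6×0.4/k)]²/d² = 9.92.
- Corrected n = (n₀/4)[1 + √(1 + 2(1+1/k)/(n₀d))]² = 12.75, so 12.75 + 25.50 = 38.2 evaluable.
- 38.2 × 1.2 = 45.9, which reproduces 46 (dividing by 0.8 gives 47.8).

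**Step 1: definitions taken literally.** Consent comes before the screening challenge, which every randomised child must fail. Each child therefore has a recorded event before allocation: 30/30 v 16/16, Fisher p = 1.0 whatever OIT does. The outcome of the logistic regression is constant.

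**Step 2: start at randomisation, month-12 challenge included.** From section 7.1, 100% − 60% = 40% of active and 100% − 10% = 90% of control attenders react below 1.4 g. A child who tolerates 1.4 g can still react at the 3000 mg step, so these are minimum reaction rates under the plan's assumptions.

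Assumptions not in the documents: 10% of controls have an accidental reaction, challenge and non-challenge reactions are independent, and 50%, 70% or 90% of active children react to OIT doses. With attendance a:

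- Active any-event rate = 1 − (1 − OIT rate)(1 − 0.4a).
- Control any-event rate = 1 − (1 − 0.1)(1 − 0.9a).

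Power below is by exact enumeration of the two-sided Fisher test at 30 v 16 and counts only rejections with the active arm worse. Rates are active v control.

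| OIT reaction rate | Challenges excluded | Month 12 included, all attend (a = 1) | Month 12 included, 20% dropout (a = 0.8) |
|---|---|---|---|
| 50% | 50% v 10%; 79% | 70% v 91%; about 0% | 66% v 75%; 0.4% |
| 70% | 70% v 10%; 99% | 82% v 91%; 0.2% | 80% v 75%; 5% |
| 90% | 90% v 10%; >99% | 94% v 91%; 4% | 93% v 75%; 41% |

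In the first row with all attending, the test rejects in 28% of trials, essentially always with controls looking worse. The month-12 challenge alone (40% v 90%) would show fewer active-arm reactions with 93% power, which is an efficacy result. The challenges held only in the active arm are not modelled and push the other way.

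Sensitivity of the challenges-excluded column to a control accidental rate of 5% to 20%: power is 93% to 46% at an OIT rate of 50%, and 99.9% to 90% at 70%.

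**Step 3: graded test.** Mann-Whitney on worst grade per child, simulated with 2,000 runs. Assumed screening grades 1/2/3 are 55/35/10%, and OIT grades are either 80/17/3% or 50/40/10%. Across OIT rates of 50% to 90%, power is 5% to 29% with the screening reaction counted and 81% to 100% without it.

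**Step 4: end of window.** Section 5.5 offers controls OIT from month 12. Without an end date, and with children analysed as allocated (7.2), their OIT reactions could count as control events.

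**The case against.** The strongest reply is that the plan never says challenge reactions count. Section 6.2 governs what is recorded, not what is analysed. Active and control groups exist only from randomisation, so counting a pre-randomisation reaction is an unlikely reading. Section 3.2 describes OIT reactions against accidental ones, and section 3.1.2 frames the outcome as the safety of OIT. Control diaries log accidental reactions (5.3.3), and OIT diaries record timing relative to the dose (5.3.4). All of this stands as evidence of intent, but no analysis rule carries it out.

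A reader might infer that the planned test cannot show harm and is forced to a null. The documents do not support that. Saturation applies to the any-event proportion on the literal reading. The graded test keeps some power, and section 6.1 has a serious-adverse-reaction category tied to OIT doses, although no comparison is defined for it. Counting from randomisation can favour either arm.

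Illustrations with assumed counts show how far the answer moves. OIT and accidental reactions alone, 27/30 v 3/16, give p = 0.000002. Adding challenge reactions to reach 29/30 v 15/16 gives p = 1.0. But 20% dropout leaves about 0.8 × 0.9 = 72% of controls reacting at month 12. With accidental reactions added, 29/30 v 12/16 gives p = 0.043.

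Nor does section 2.2 name a control comparison in the safety objective. That link comes from sections 3.2 and 7.2.2.

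**Conclusion.** The concern holds as a gap with real consequences. The stated definitions, followed literally, give an any-event comparison of 100% v 100% and a regression with no variation. Starting at randomisation is not enough: under the stated assumptions, power to show harm at OIT reaction rates of 50%, 70% and 90% falls from 79%, 99% and >99% to about 0%, 0.2% and 4% with full attendance, or 0.4%, 5% and 41% with 20% dropout. The comparison then partly measures efficacy and the challenge schedule.

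The 40% and 90% follow from the plan's own rates. The accidental-reaction rate, the OIT reaction rates, independence and the grade distributions are assumptions. The size and direction of bias depend on them and on attendance, so neither a forced null nor a complete inability to show harm is established. This is a secondary safety analysis, and the primary endpoint and sample size are untouched: a should-fix.

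**What to change.** In section 7.2.2:

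1. Define the between-arm comparison as adverse events from randomisation to just before the first month-12 DBPCFC day, which is also before controls may start OIT. State a 12-month cut-off for children who do not attend that challenge.
2. Exclude reactions during any protocol food challenge and those found at the next-day follow-up. Supervised updosing doses are OIT doses, so reactions to them stay in.
3. Use the same event set for the Fisher test, the graded test and the logistic regression.
4. Tabulate challenge reactions separately by challenge (screening, boiled-peanut entry challenge, transition, month 12, month 13) and eliciting dose.

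The cost is analysis-plan wording. Challenge days are known, next-day contact is already planned (5.2.2), and diaries record timing relative to the dose. The case report form is not in the documents; I assume it dates each event. No visit, dose or sample-size change is needed.
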